6.0 Procedures Involved*

Recruitment/Sampling: Patients will be recruited using convenience sampling technique from HIV primary care clinics with whom the PI works regularly: the Columbia County Department of Health (Lake City, FL) and the CAN Community Health Clinic (Jacksonville, FL)

Preliminary Screen: Patients will be prescreened for eligibility using a computerized screening tool, NIDA Modified Alcohol, Smoking, Substance Involvement Screening Test [NM-ASSIST], to assess substance misuse risk level. All clinic patients will have the opportunity to complete the substance use screening assessment after checking in for their appointment. All who score moderate and above on the alcohol or illicit substance portion of the NM-ASSIST and meet eligibility criteria will be referred to the study. We will train all recruiters (clinic staff) to provide an extensive explanation of why we are offering these services, as the patients may not perceive themselves as having a substance misuse issue.

Baseline Assessment Procedures: Following a successful initial screen, study staff will explain the procedures of the study and obtain informed consent. All study activities will be conducted in a private room in the clinic. The research assistant (RA) performing the assessment will verify the patient's complete understanding of the informed consent form and all study procedures. Following informed consent, patients will complete the baseline assessment. The baseline assessment will consist of urine drug screen and a series of research questionnaires delivered on a mobile device. The research questionnaires include information on: substance use, substance use treatment, HIV treatment engagement, depression, and pain. The assessment is relatively brief in order to maximize willingness to participate and decrease patient burden. The assessment will take approximately 30 minutes to complete. The questionnaires will be given in a computerized. The iPad/tablet will use REDCap survey software, which provides direct, encrypted transfer of information via internet to a secure study server.

Three and Six Month Follow-Up Assessment: *Participants will be contacted three and six months post-intervention to schedule an in-person follow-up assessment. We will evaluate substance use treatment engagement post intervention and substance use (self-report and urine toxicology analysis). Participants will be compensated \$30 for each*

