Randomization: We will use Block random assignment (blocks of 4 by each recruitment site) to ensure equal numbers are assigned to each condition by site. Randomization should create groups with equal characteristics with respect to disease related and medical variables. However, we will assess for baseline differences prior to conducting any analyses and control as necessary.

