10.0 Subject Population*

Participants will be 90 patients recruited through DOH Columbia County and CAN Community Health.

Study inclusion criteria includes that patients must be:

1. HIV-positive (seropositive confirmed by medical records).
2. Arrive for a clinic visit with an HIV physician.
3. Have a substance misuse screening score indicating moderate or high risk.

Persons will be ineligible if they:

1. are unable to interview and consent in English
2. unwilling or unable to participate in follow up
3. currently in addiction treatment
4. have a medical marijuana prescription

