To examine ratings of acceptability, we will use the overall acceptability score and percentage of acceptability. Overall acceptability will be assessed by summing ratings from the 10-item questionnaire to provide a total intervention acceptability score for the intervention, such that acceptability scores for the intervention could range from 10 (low acceptability) to 50 (high acceptability). The intervention will be considered to have acceptability if 80% of the participants rank the intervention as acceptable (i.e., 4 or higher) on 80% or more of the scale items. We will then examine each question of the Acceptability Questionnaire separately to determine strengths and weaknesses of the intervention.

Aim 2a and 2b (Acceptability): Acceptability scores will be calculated for all participants as listed above to determine overall acceptability of the SBIRT model. Sub analyses will be conducted for disease type and HIV x age using calculations listed above. Acceptability will be examined by disease type HIV vs. non-HIV. Acceptability will also be examined for HIV only by younger (≤ 49) versus older (≥ 50).

Aim 3: We will clean the data, examine variable distributions, compute descriptive statistics, examine outliers, and examine the effectiveness of randomization prior to analyses of specific aims to ensure the underlying assumptions of normality and equal variance have not been violated. Before testing each secondary outcome, we will examine whether intervention and control group participants differ on potential confounding variables at study entry. We will control for a variable if it differs by condition on the outcome variable being tested in that analysis at $p < .05$. Using chi-square (or t-test for continuous variables) we will examine the associations between the dependent variables and relevant demographic variables. All analyses will employ an intent-to-treat approach.

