Our first step will be to see if the intervention influenced formal engagement in substance use treatment. Using chi-square analyses we will examine group difference on engagement in formal treatment (0=no treatment/1=treatment confirmed). To test the remainder of the hypothesis, analyses will rely on mixed model repeated measures ANOVA since the relatively small sample size is likely to prohibit more sophisticated statistical modeling. Hypotheses testing rely on inspection of F values and associated p values. A mixed model ANOVA is used to test for differences between two or more independent groups while subjecting participants to repeated measures. In the current analyses the fixed effect will be group condition (SBIRT-PN or TAU) and the random effect will be number of drug use days in the past 3 and 6 months.

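### Randomisation is blocked within two clinics but no Aim 3 test uses site, so the tests can be conservative and lose power if the clinics differ substantially

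*SAP*

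**What the plan says.** **Design.** Protocol section 6.0, under Randomization: "We will use Block random assignment (blocks of 4 by each recruitment site) to ensure equal numbers are assigned to each condition by site". The sites are "the Columbia County Department of Health (Lake City, FL) and the CAN Community Health Clinic" in Jacksonville. Section 10.0 gives the total: "Participants will be 90 patients recruited through DOH Columbia County and CAN Community Health". The split between the clinics is not stated.

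**Engagement test.** The SAP, Aim 3, has: "Using chi-square analyses we will examine group difference on engagement in formal treatment". No stratification is mentioned.

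**Drug-use model.** The SAP describes a mixed-model repeated-measures ANOVA and then: "In the current analyses the fixed effect will be group condition (SBIRT-PN or TAU"). No other fixed effect is named. Protocol section 17.0 (Analysis Plan, Aim 3) has the same text for both tests.

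**Route to adjustment.** The SAP and protocol section 17.0 share one conditional rule, applied at p < .05: "We will control for a variable if it differs by condition on the outcome variable being tested". Section 6.0 also allows control for baseline differences as needed. Neither names site. The missing-data steps in section 17.0 use predictors of dropout for imputation, but do not put site into the tests.

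**The concern.** Blocking within site removes site differences from the comparison of the arms. An analysis that ignores site still counts those differences as noise. The standard error is then larger than the true sampling variation of the group difference, the test rejects less often than its nominal level, and power falls.

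The adjustment rule selects variables by imbalance, and stratified blocking removes imbalance. A reader who expects the rule to pick up site if it matters would be wrong: a factor can predict the outcome strongly and still be perfectly balanced. With 90 patients and a maximum dropout of 20% (section 25.0, Retention), any power that can be recovered by wording alone is worth having.

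**Working it through.** **Inputs from the documents:** N = 90, 1:1, two sites, blocks of 4 within site. At 20% dropout, 90 × 0.8 / 2 = 36 per arm.

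**Assumptions:** two-sided 0.05 and sites of similar size; all site rates, site gaps and treatment effects. The plan gives no power calculation, so it has no figure to reproduce.

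**Step 1. Can the p < .05 rule select site?** An unfinished block of 4 leaves an imbalance of at most 2 at a site.
- Sites of 46 and 44, worst split 24/22 and 22/22: chi-square = 90 × (24×22 − 22×22)² / (46×44×46×44) = 0.04, p = 0.84.
- Extreme case, sites of 2 and 88, split 2/0 and 44/44: chi-square = 90 × (2×44 − 0×44)² / (2×88×46×44) = 1.96, p = 0.16.

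Among all randomised patients, the set for an intent-to-treat analysis, the rule does not select site.

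**Step 2. Between-group comparison of drug-use days.** Let D be the site gap in within-site SDs. With equal sites the unadjusted standard error is too large by f = √(1 + D²/4). The true level is 2 × [1 − Φ(1.96 f)]. For a test with 80% power when site is in the model (1.96 + 0.84 = 2.80), power without site is 1 − Φ(1.96 f − 2.80).

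| D | f | True level | Power without site |
|---|---|---|---|
| 0.5 | 1.031 | 4.3% | 78% |
| 1.0 | 1.118 | 2.8% | 73% |

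With an assumed effect of 0.6 SD and 36 per arm, power is 72.1% with site; without it, 70.0% (D = 0.5) or 63.8% (D = 1.0).

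**Step 3. Group-by-time reading.** A site gap that is constant over visits drops out of each patient's change from baseline. In simulation with a 0.5 SD effect and D = 1.0, power for the change was 76.7% with or without site.

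**Step 4. Engagement.** The pooled chi-square uses the variance p̄(1 − p̄); the variance that applies within sites is the average of p(1 − p) over sites. With no treatment effect:
- 10%/20%: 0.1275 against 0.125, ratio 1.02.
- 10%/30%: 0.16 against 0.15, ratio 1.07.
- 10%/60%: 0.2275 against 0.165, ratio 1.38.

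Small gaps hardly matter; large ones do. Simulation (at least 100,000 trials per scenario, sites of 44 and 46, 1:1 within site) gives a true level for the pooled test of about 5.3% (10%/20%), 4.7% (10%/30%), 4.0% (10%/40%) and 2.4% (10%/60%). The Cochran-Mantel-Haenszel (CMH) test without continuity correction stays at about 5% throughout. Power:

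| Site 1, control to SBIRT-PN | Site 2, control to SBIRT-PN | Chi-square | CMH |
|---|---|---|---|
| 10 to 28% | 20 to 45% | 67.5% | 67.1% |
| 10 to 28% | 30 to 60% | 71.9% | 73.6% |
| 5 to 20% | 40 to 68% | 61.5% | 69.1% |
| 5 to 25% | 45 to 75% | 72.4% | 81.1% |
| 10 to 30% | 60 to 85% | 57.0% | 73.1% |

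With a continuity correction, CMH power in the last three rows is about 59%, 73% and 64%. Most or all of the gain is then lost.

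**The case against.** Several objections limit the point.

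- **Size.** A reader might infer that power is lost whenever the clinics differ. That does not follow: the first row of the table shows no loss. The large losses need control rates 35 to 50 points apart, and nothing in the documents supports gaps of that size. Both sites are HIV primary care clinics in Florida, and section 10.0 sets the same eligibility for both, including no current addiction treatment. This stands.
- **Drug use.** A reader might infer that both parts of H3 lose power. The model has repeated measures, the design includes a baseline, and H3 speaks of a reduction in use. If the test is group-by-time, a constant site gap costs nothing. The SAP names only group as the fixed effect and no interaction, so either reading is open and the loss in step 2 is conditional.
- **Direction.** Ignoring a blocking factor might be taken to bias the result or produce false positives. It does neither; the error is on the cautious side.
- **Single-clinic effects.** The lack of results by site might be seen as a flaw. With about 22 patients per arm per site (90 / 4), such tables could not separate an effect in one clinic from chance, and the plan does not prevent them. They are a reporting preference.
- **Complexity.** The plan says that its small sample is likely to rule out more elaborate models. This does not excuse the omission: a stratified test of a 2×2 table is no harder than a chi-square, and site takes one degree of freedom.

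**Conclusion.** The omission is real: site is a stratification factor, no Aim 3 test uses it, and the plan's adjustment rule cannot supply it. The consequence is conditional and conservative.

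For engagement, the loss runs from nil (control rates about 10 points apart) through about 2 points (10%/30%) to about 8 to 16 points (gaps of 35 to 50 points). For a main-effect comparison of drug-use days it is about 2 points at a 0.5 SD gap and 7 points at 1 SD, from 80%. For a group-by-time test with a constant gap it is nil. These figures rest on assumed gaps and effects, sites of similar size and a two-sided 0.05 level.

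Aim 3 is secondary in a feasibility pilot with no stated power target, so the point is minor: worth making because it is free, not because the result is at risk of being wrong.

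**What to change.** In the SAP (Aim 3) and protocol section 17.0 (Analysis Plan, Aim 3):

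1. Replace the chi-square for engagement with a Cochran-Mantel-Haenszel test stratified by recruitment site. State that no continuity correction is used. Logistic regression with group and site is an alternative.
2. Include recruitment site as a fixed effect in the repeated-measures model, whatever the p < .05 rule returns.

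The cost is wording and one degree of freedom in the model. Blocking by site already requires each patient's site to be known, so no new data are needed.

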1.0 Study Summary

Study Title	Feasibility of Screening, Brief Intervention for HIV+ Adults 50+ in Primary Care Settings
Study Design	We will use a repeated measures randomized control trial design to compare patient outcomes at baseline as well as 3 and 6 months post-intervention.
Primary Objective	Feasibility and Acceptability of intervention
Secondary Objective(s)	Substance misuse
Research Intervention(s)	Screening, Brief Intervention, Referral to Treatment with Peer Navigator (SBIRT-PN)
Study Population	HIV+
Sample Size	90
Study Duration for individual participants	6 months
Study Specific Abbreviations/ Definitions	SBIRT-PN = Screening, Brief Intervention, Referral to Treatment with Peer Navigator

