Substance Use Treatment Engagement: Participants will self-report if they obtained formal substance use treatment (i.e., any services sought to address substance use from individual therapy to 12 step fellowships). We will request treatment facility information and permission to verify treatment. Once treatment has been verified, treatment engagement will be coded as 0= no formal treatment 1= formal treatment engagement

Substance use NIDA STTR Drug and Alcohol Use Measure: A standard measure from the NIDA STTR Vulnerable Populations Data Harmonization tool kit will be used. It will assess quantity and frequency of types of substances used in the prior 30 days.

Biologically Confirmed Drug Use: A CLIA 12-Panel Instant Drug Test Cup (CLIAwaived™, San Diego, CA), which tests for the presence of 12 common substances in the urine will be used.

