17.0 Data Management* and Confidentiality

Analysis Plan

Aim 1: Feasibility will be calculated as described above. The model will be considered feasible if 80% of the target population has been reached.

Aim 2: Acceptability scores will be calculated for all participants as listed above to determine overall acceptability of the SBIRT model. Sub analyses will be conducted for disease type and HIV x age using calculations listed above. Acceptability will be examined by disease type HIV vs. non-HIV. Acceptability will also be examined for HIV only by younger (<49) versus older (>50).

Aim 3: This pilot is a randomized two groups (SBIRT-PN vs. TAU) with repeated measures (baseline and 3 and 6-month follow-ups) design. We will clean the data, examine variable distributions, compute descriptive statistics, examine outliers, and examine the effectiveness of randomization prior to analyses of specific aims to ensure the underlying assumptions of normality and equal variance have not been violated. Before testing each secondary outcome, we will examine whether intervention and control group participants differ on potential confounding variables at study entry. We will control for a variable if it differs by condition on the outcome variable being tested in that analysis at $p < .05$. Using chi-square (or t-test for continuous variables) we will examine the associations between the dependent variables and relevant demographic variables. All analyses will employ an intent-to-treat approach.

Our first step will be to see if the intervention influenced formal engagement in substance use treatment. Using chi-square analyses we will examine group difference on engagement in formal treatment (0=no treatment/1=treatment confirmed). To test the remainder of the hypothesis, analyses will rely on mixed model repeated measures ANOVA since the relatively small sample size is likely to prohibit more sophisticated statistical modeling. Hypotheses testing rely on inspection of F values and associated p values. A mixed model ANOVA is used to test for differences between two or more independent groups while subjecting participants to repeated measures. In the current analyses the fixed effect will be group condition (SBIRT-PN or TAU) and the random effect will be number of drug use days in the past 3 and 6 months.

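### The Aim 3 model sentence labels drug use days the random effect and leaves open which F value decides the substance-use part of H3 and how baseline enters

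*SAP*

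**What the plan says.** For the part of H3 that concerns substance use, the SAP (Aim 3) and Protocol 17.0 (Analysis Plan, Aim 3) give the same text. The method is a mixed model repeated measures ANOVA, described as a way to "test for differences between two or more independent groups while subjecting participants to repeated measures". Group (SBIRT-PN or TAU) is the only fixed effect named, and "the random effect will be number of drug use days in the past 3 and 6 months". The decision rule is: "Hypotheses testing rely on inspection of F values and associated p values".

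On timing, Protocol 1.0 says the design will "compare patient outcomes at baseline as well as 3 and 6 months post-intervention", and Protocol 17.0 calls it a "repeated measures (baseline and 3 and 6-month follow-ups) design". The SAP does not carry that design sentence, and the model sentence in both documents mentions 3 and 6 months only.

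On covariates, both documents adjust for a variable only if the arms differ on it at p < .05. That threshold is the only one given; no significance level is stated for the H3 tests.

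On the outcome, Protocol 4.0 describes a drug and alcohol measure covering "quantity and frequency of types of substances used in the prior 30 days", and lists a urine drug test as well. Protocol 6.0 has both self-report and urine collected at follow-up, and allows entry on alcohol risk.

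**The concern.** H3 predicts a reduction in substance use, so drug use days is the response. A response cannot be a random effect in its own model. In a repeated measures ANOVA the random factor is the participant and visit is a within-participant factor; neither is assigned here, nor is group-by-visit.

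The slip matters because correcting it does not yield a single analysis. Two things stay open.

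1. **Which F decides.** A two-group, three-visit ANOVA gives a group F and a group-by-visit F. Group is the only effect the text names, but the plural F values and the three-visit design exclude neither.
2. **What baseline does.** It could be a repeated level, a covariate, or absent from the model. If it is not a repeated level, and if it counts among the variables checked for imbalance, the p < .05 rule makes adjustment for it depend on the data.

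The outcome is also loosely specified. The reference to 3 and 6 months can mean visits or recall windows. The model sentence covers drug use days only, with no word on how alcohol or urine results bear on H3.

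**Working it through.** The documents give no power, effect size or SD for Aim 3, so there is no figure of theirs to reproduce.

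**Inputs from the documents.** 90 participants, blocks of 4 within site, so about 45 per arm (Protocol 6.0, 10.0). Visits at 0, 3 and 6 months. Maximum dropout 20% (Protocol 25.0), so 90 × 0.8 = 72 completers, or 36 per arm.

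**Assumed, not in the documents.** A two-sided 5% level; normal data with equal correlation r between visits; for the power figures, a 0.5 SD difference at both follow-ups and none at baseline.

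**Step 1: error rate if either F may decide.** This needs no effect size. Under the stated conditions the group F (between participants) and the group-by-visit F (within participants) are independent:

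- any direction: 1 − 0.95² = 0.0975 (a 20,000-trial simulation at r = 0.5 gave 0.101);
- in the direction H3 predicts: 1 − 0.975² = 0.0494, against 0.025 for one test.

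**Step 2: what the three-visit group F estimates.** With a constant follow-up effect d, the average over visits is (0 + d + d)/3 = 2d/3, because the pre-treatment visit is averaged in. This does not depend on r.

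**Step 3: illustrative power.** With n = 45, d = 0.5, r = 0.5 and λ = (n/2) × effect² / variance:

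- (a) Group over 0/3/6 months: effect 0.333, variance (1 + 2r)/3 = 0.667, λ = 22.5 × 0.111/0.667 = 3.75, df 1 and 88. Power 48%.
- (b) Group-by-visit over 0/3/6 months: squared deviations of (0, 0.5, 0.5) from their mean sum to 0.167; λ = 22.5 × 0.167/(1 − r) = 7.5, df 2 and 176. Power 68%.
- (c) Group over months 3/6: variance (1 + r)/2 = 0.75, λ = 22.5 × 0.25/0.75 = 7.5, df 1 and 88. Power 77%.
- (d) As (c), always adjusted for baseline: variance 0.75 − r² = 0.50, λ = 11.25, df 1 and 87. Power 91%.

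| n per arm, r | (a) | (b) | (c) | (d) |
|---|---|---|---|---|
| 45, 0.3 | 57% | 53% | 83% | 88% |
| 45, 0.5 | 48% | 68% | 77% | 91% |
| 45, 0.7 | 42% | 89% | 72% | 97% |
| 36, 0.5 | 40% | 57% | 68% | 84% |

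The last row is for completers only, whereas Protocol 17.0 plans imputation. The ordering is not universal: (a) exceeds (b) at r = 0.3, and (b) exceeds (c) at r = 0.7.

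**Step 4: how often (a) and (b) would disagree.** By independence, at n = 45 and r = 0.5: 0.482 × 0.320 + 0.680 × 0.518 = 0.51. For the assumed effect, the two F values of the same model would give opposite answers on significance in about half of trials.

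**Step 5: the p < .05 rule.** Under randomisation, baseline drug use would differ at that level in about 5% of trials. If the rule governs it, baseline would be left out in the other 95% or so.

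**The case against.** The best reply is that the sentence is a slip any analyst would read through. The ANOVA label and its stated purpose supply the participant term and the outcome. Group is the one effect named, and the months named are 3 and 6. Taken literally, that is reading (c), a valid test. The group-by-visit F behind the 9.75% appears nowhere in the text; it is inferred from the type of model. And this is a secondary aim in a pilot that makes no power claim.

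Much of this stands. It would be wrong to say that the plan names no effect. What it does not settle is why the decision rests on F values in the plural, or what happens to a baseline visit that the Protocol twice counts as part of the design.

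A reader might also infer more than the documents support:

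- *That no valid test of H3 can be had from the plan.* Not so; reading (c) is one.
- *That 9.75% is the chance of wrongly confirming H3.* H3 is directional, so the relevant figure is about 4.9% against 2.5%. Both rest on an assumed 5% level.
- *That the mislabelling costs the gap between 77% and 91% power.* It does not. Adjusting for baseline is an efficiency gain available to any version of the analysis.
- *That the model contradicts the 30-day measure.* It does only if the 3 and 6 months are recall windows. If they are visits, there is no mismatch.
- *That the p < .05 rule certainly governs baseline drug use.* The documents speak of potential confounders and do not say whether baseline drug use is among them.

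**Conclusion.** The concern holds in a limited form and should be fixed. The model statement is wrong as written in both documents. The literal reading is usable, but the text does not bind the analyst to it.

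The size is a doubling of the false-positive rate if either F of the three-visit model may decide. This rests on an assumed two-sided 5% level, normality and equal correlation between visits. The shrinkage to two-thirds under the three-visit group F needs only a follow-up effect that is constant and absent at baseline. The power figures are illustrations on assumed values and show only that the choice of F matters.

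The consequence is confined to the substance-use part of H3. Feasibility, acceptability and the chi-square test of treatment engagement do not depend on this sentence.

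**What to change.** In both documents, replace the model sentence with text such as:

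> Dependent variable: drug use days in the prior 30 days, derived from the Protocol section 4.0 measure, at months 3 and 6. Fixed effects: group, visit, group-by-visit, baseline value of the same variable (included whether or not the arms differ) and site (the randomisation stratum). Random effect: participant. The substance-use part of H3 is decided by the group difference averaged over months 3 and 6, two-sided 5%; all other F values, and the alcohol and urine results, are supportive.

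Another single contrast named in advance would also remove the ambiguity. The essentials are one deciding test, its significance level and a stated role for baseline.

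Four points go with it:

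- If the sponsor wants alcohol use to count towards H3, say so and name the one deciding outcome.
- Confirm that the measure yields days of use; Protocol 4.0 promises quantity and frequency only.
- If the 3 and 6 months are visits, say at months 3 and 6.
- If outcome data by arm have already been examined, report the choice as post hoc.

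The cost is wording changes in two documents and one or two degrees of freedom for the covariates. No new visit is needed, and no new measure provided that the planned one yields days of use.
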